8.4 Handling of efficacy data (ClinRO and PRO) and imputation strategy

8.4.1 Data handling and visit windows for analysis

After occurrence of an intercurrent event (such as use of rescue medication or systemic SoC) the analysis will be performed according to the estimands. Data collected after use of topical rescue medication or systemic SoC are likely to show improvement in efficacy assessments. Such favourable values should not be included for analysis (unless stated otherwise, i.e. for the analysis of the effect of study intervention and rescue medication combined).

Therefore, the following first data handling step will be performed for participants who use systemic SoC or who use topical rescue medication at or after Day 56 (Visit 6) (or Day x (Visit x) for supplementary analyses):

All efficacy assessments (ClinRO or PRO) collected after (i.e. on the next day or later) first start of systemic SoC or start of topical rescue medication at or after Day 56 (Visit 6) (or Day x (Visit x) for supplementary analyses) will be set to missing (including FU visit). In case of use of rescue medication at Day 56 (Visit 6) (or Day x (Visit x) for supplementary analyses) which already started before that day the assessments after start of rescue medication will be set to missing as well.

This refers to use of any medication from the systemic SoC list and topical rescue medication list in Section 8.3 no matter if the medication was adjudicated as intercurrent event "use of systemic SoC" / "use of rescue medication at or after Day 56 (Visit 6)" as described in Section 8.3 or not.

Then the following data handling steps will be performed for all participants:

Efficacy assessments (i. e. ClinRO and ePRO weekly average of Peak Pruritus 0-10 NRS) at planned visits will be considered valid for analysis if they fall in the following visit windows (for Peak Pruritus the assessments at the actual visit days will be checked):

Day 1 (Visit 3)	Day 1*
Day 14 (Visit 4)	[Day 10, Day 18]
Day 28 (Visit 5)	[Day 21, Day 35]
Day 56 (Visit 6)	[Day 49, Day 63]
Day 84 (Visit 7)	[Day 76, Day 92]
FU (Visit 8)	no restriction

Table 8-3: Visit windows for analysis

* If the efficacy assessment is done at Day 1 (Visit 3) but treatment is started later, the assessment will also be acceptable.

[figure not shown]
Likewise, valid values from end of treatment visits and unscheduled visits can be assigned to the respective planned visits if they fall into the visit window as listed above. If several assessments fall into the same visit window the one closer to the planned visit day will be taken unless rescue medication was taken before at least one of the assessments. If there is still an assessment(s) without prior rescue medication use the one closest to the planned visit day will be selected. Otherwise, the one with greater distance to prior rescue medication use will be selected. (If there should be two assessments with equal distance to the planned visit date and not affected by rescue medication use then the one assessed at the regular visit will be taken.) Assessments from end of treatment visits after early discontinuation of study drug will only be considered for assignment to a planned visit if the end of treatment visit was not later than three days after last study drug intake.

[figure not shown]
Especially, it will be checked according to the criteria specified above if data from an early discontinuation visit or unscheduled visit before the use of rescue medication at Day 56 (Visit 6) (or Day x (Visit x) for supplementary analyses) or use of systemic SoC is available which fulfills the rules defined above. Likewise, in case of early discontinuation due to lack of efficacy or due to other reasons it will be checked if data from an early discontinuation visit or unscheduled visit before the intercurrent event is available which fulfills the rules defined above. If so, these values will be assigned to the respective planned visit.

Imputation of efficacy data for visits after an intercurrent event will be described in Section 8.4.2 and 8.4.3.

Note that events of "use of topical rescue medication" and "use of systemic standard of care" which are not considered intercurrent events as described in Section 8.3 (i. e. if the medication was not used for treatment of AD) will be handled and imputed as described for the intercurrent event "discontinuation of study intervention due to other reasons" (refer to Section 8.3).

[figure not shown]
Furthermore, if a regular visit at Day 56 (Visit 6) (or Day x (Visit x) for supplementary analyses) (i.e. a visit in the respective visit window for analysis as stated above) is changed into an end of treatment visit and rescue medication is taken at that visit this will be handled similarly to "use of rescue medication at or after Day 56" (or Day x (Visit x) for supplementary analyses) for analysis.

[figure not shown]

[figure not shown]

CONFIDENTIAL

CCI	
	1
_	
	l
	1
	1

CCI

CONFIDENTIAL	Statistical Analysis Plan BAY 1834845 / 22158	
	Version 1.0	Page: 69 of 72
С		
CI		

Page: 70 of 72

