8.1 Administrative and General Procedures

- Study procedures and their timing are summarized in the SoA (Section 1.3). Protocol waivers or exemptions are not allowed.
- Immediate safety concerns should be discussed with the sponsor immediately upon occurrence or awareness to determine if the participant should continue or discontinue study intervention.
- Adherence to the study design requirements, including those specified in the SoA, is essential and required for study conduct.
- All screening evaluations must be completed and reviewed to confirm that potential participants meet all eligibility criteria. The investigator will maintain a screening log to record details of all participants screened and to confirm eligibility or record reasons for screening failure, as applicable.
- Procedures conducted as part of the participant's routine clinical management (e.g., blood count) and obtained before signing of the ICF may be utilized for screening or baseline purposes provided the procedures met the protocol-specified criteria and were performed within the time frame defined in the SoA.
- Laboratory/analyte results that could unblind the study will not be reported to investigative sites or other blinded personnel until the study has been unblinded.
- Patient-reported outcomes as listed in Section 8.2.2 will be provided in local language, and in the case of completion at the study site they should always be completed by the study participants prior to any activities at site.
- In the event of a significant trial-continuity issue (e.g., caused by a pandemic), alternate strategies for participant visits, assessments, medication distribution and monitoring may be implemented by the sponsor or the investigator, as per local health authority / ethics requirements.

The maximum amount of blood collected from each participant over the duration of the study, including any extra assessments that may be required, is not expected to exceed 180 mL. Repeat or unscheduled samples may be taken for safety reasons or for technical issues with the samples.

Unscheduled visit(s)

Participants who experience a suspected AD flare/relapse between scheduled study visits will return to the clinic for an unscheduled visit to determine if AD flare/relapse is confirmed

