Single subjects without any valid post-dose value in the treatment phase according to Section 8.4.1 (e. g. which discontinued treatment before first post-dose visit at Day 14 (Visit 4) due to lack of efficacy or took rescue medication at all visits until treatment discontinuation) will be included in the mixed model by using last observation carried forward for Day 14 (Visit 4) to avoid bias. Post-dose values from unscheduled visits or early discontinuation visits will be considered irrespectively of any time windows (but early discontinuation visits will only be considered if study intervention was not stopped earlier than 3 days ago). Otherwise, the baseline value will be carried forward.

Additionally for the same scenarios as for the mixed effect repeated measurement model, multiple imputation using linear regression will be performed using the multiple imputation procedure (PROC MI) from SAS based on the following variables: treatment, absolute EASI score at Day 1 (Visit 3), Day 14 (Visit 4), Day 28 (Visit 5), Day 56 (Visit 6), Day 84 (Visit 7). The fully conditional specification (FCS) method will be used in such a way that for each imputed continuous variable, all preceding variables will be considered. The seed will be 6345 and 50 imputations will be performed. Imputed values will be restricted to the range of possible values using the minimum and maximum options of SAS multiple imputation procedure (i. e. if values are imputed outside of the possible range, another value will be re-

drawn for imputation). The missing data pattern and variance information outputs for the multiple imputation will be presented in Section 10 of the CSR.

All participants from the PPS or FAS, respectively, will be included.

If the linear regression will not be possible for both treatment groups due to scarcity of data especially at later time points the imputation will only be performed for the zabedosertib group.

Subsequently, an analysis of covariance (ANCOVA) as described above will be performed by visit for all visits as planned.

The mean estimates for percent change of EASI score at Day 84 (Visit 7) by treatment and the difference between treatments as derived from the ANCOVA model or mixed model of repeated measures analysis as described above will be plotted including 95% confidence intervals for all analyses as summarized in Table 4-2.

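### An unscheduled EASI taken after the end of treatment can replace a completer's scheduled Visit 7 score as the primary Day 84 value under the readable rules of SAP 8.4.1

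*SAP*

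**What the plan says.** The primary endpoint is EASI 75 response at Day 84 (Visit 7). The Protocol schedule of activities (1.3) places Visit 7, the end-of-treatment visit, at Day 84 ±3. SAP Table 8-3 accepts values from Day 76 to Day 92 for that slot.

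The rules of SAP 8.4.1 for filling the slot are:

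- **Sources:** "valid values from end of treatment visits and unscheduled visits can be assigned to the respective planned visits if they fall into the visit window".
- **Several values, no rescue:** "If several assessments fall into the same visit window the one closer to the planned visit day will be taken".
- **All values preceded by rescue:** "Otherwise, the one with greater distance to prior rescue medication use will be selected".
- **Exact tie, unaffected by rescue:** "then the one assessed at the regular visit will be taken".
- **On-drug limit:** "Assessments from end of treatment visits after early discontinuation of study drug will only be considered for assignment to a planned visit"; the condition is a gap of at most three days from the final dose.

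SAP 4.1.2 words the limit for early discontinuation visits. SAP 4.4.2 does the same for the mixed model: "but early discontinuation visits will only be considered if study intervention was not stopped earlier than 3 days ago".

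Protocol 8.1 says when unscheduled visits arise: "Participants who experience a suspected AD flare/relapse between scheduled study visits will return to the clinic for an unscheduled visit". Under the primary estimand (SAP 1.1), topical rescue before Day 56 is disregarded, so such participants are still classified on their Day 84 EASI.

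**The concern.** The SAP treats an EASI from an early discontinuer as unusable for a planned visit once more than three days have passed since the last dose. It states no equivalent condition for a completer's unscheduled visit, although the Day 84 window stays open for several days after dosing has ended. The check for values before an intercurrent event does not help, because regular completion is not an intercurrent event.

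A participant who met EASI 75 at Visit 7 could thus be scored on a later assessment made off treatment. Since suspected flares lead to unscheduled visits, that assessment may well be a flare score. The primary variable would then no longer describe the end of the 12-week treatment period for that participant. With 38 and 19 evaluable participants, single reclassifications can matter.

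**Working it through.** **Inputs.** Visit 7 tolerance Day 81-87 (Protocol 1.3). Analysis window Day 76-92 (SAP Table 8-3). Selection rules from SAP 8.4.1. 38 vs 19 evaluable, rates 0.49 vs 0.16, success if the posterior probability exceeds 0.90, Beta(1,1) priors (SAP 2, 4.2.2 and 5). Assumption: the last dose is on the day of Visit 7. The schedule footnotes support this, since the morning dose at visits with PK sampling is taken on site.

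**The plan's own figure.** Enumerating both binomials exactly with Beta(k+1, n−k+1) posteriors gives a power of 0.910, which agrees with the stated minimum of 90%.

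**Route 1: no rescue.** Let v be the day of Visit 7 and u > v the unscheduled day. The unscheduled score wins if |u − 84| < |v − 84|.

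| Visit 7 | Winning unscheduled days | Pairs | More than 3 days after Visit 7 |
|---|---|---|---|
| Day 81 | 82-86 | 5 | 2 (Days 85, 86) |
| Day 82 | 83-85 | 3 | 0 |
| Day 83 | 84 | 1 | 0 |
| Day 84-87 | none | 0 | 0 |

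That is 9 replacing pairs, of which 2 exceed three days off drug. If Visit 7 falls outside the protocol tolerance but inside the SAP window, Day 76 is the extreme: an unscheduled visit up to Day 91 wins, and Day 92 ties and goes to the regular visit. Over the whole window there are 64 replacing pairs, 42 of them beyond three days.

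**Route 2: rescue before Day 56.** Both scores follow the rescue. If prior rescue use has no look-back limit, the later score always has the greater distance, so every u from v + 1 to 92 wins, even over a Visit 7 on Day 84. For Visit 7 on Days 81 to 87 the pairs number 11 + 10 + 9 + 8 + 7 + 6 + 5 = 56. Those more than three days apart number 8 + 7 + 6 + 5 + 4 + 3 + 2 = 35.

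These are counts of possible day combinations, not probabilities.

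**Effect on the decision.** Take 3/19 on placebo (0.158, close to the planned 16%):

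- 13/38 vs 3/19: P = 0.918, criterion met.
- 12/38 vs 3/19: P = 0.885, criterion not met.
- 12/38 vs 2/19: P = 0.953, criterion met. Here a placebo responder is the one lost.

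With the planned minimum of 100,000 draws, the simulation error near 0.90 is √(0.9 × 0.1 / 100,000) = 0.00095, so none of these three results depends on it. Weighting all outcomes by their probability at 0.49 vs 0.16, the loss of one zabedosertib responder changes the decision in about 3.9% of trials.

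**The case against.** **Most of Route 1 is on treatment by the SAP's own standard.** This stands. Within the protocol tolerance, 7 of the 9 replacing pairs lie within three days of the assumed last dose. A reader might infer from the window that any unscheduled EASI up to Day 92 can displace Visit 7. Without rescue it cannot, and with Visit 7 on Day 84 or later it never does.

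**Route 2 rests on one reading.** This also stands. SAP 8.4.1 does not define prior rescue use, and the imputation rules in SAP 4.2.2, 4.2.3 and 4.3.2 use a seven-day look-back. If that look-back was meant here too, an early rescue would not govern the Day 84 choice. The text does not say so.

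**Something may be hidden.** Figures are missing from 8.4.1, and the pages after it are redacted. SAP 4.1.1 also keeps follow-up visit data out of the Bayesian analysis. A further rule may exist, so the finding is limited to the readable text. That text, however, lists unscheduled visits as a source for planned visits and does not assign post-treatment ones to follow-up.

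**The direction is not established.** It is tempting to conclude that the error works against zabedosertib. Loss of effect through drug withdrawal can arise only on zabedosertib, but the Protocol (2.2.1) describes AD as relapsing, and the sample size assumes some placebo responders. These can flare after Visit 7 and be overwritten too, which would favour zabedosertib.

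**Conclusion.** The point holds for completers, on the readable text. SAP 8.4.1 contains a selection rule that can put a post-treatment unscheduled EASI in place of an available Visit 7 score for the primary endpoint. For early discontinuers, the existing three-day limit and the check for values before the intercurrent event largely close the route.

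The effect is probably small. Harm requires a completer with an unscheduled EASI shortly after Visit 7, a response status that differs between the two scores, and one of the two routes. The documents give no frequency for this, and the net direction is unknown. Nor do they support the inference that one reclassified participant would usually decide the trial: at the planned rates the loss of one zabedosertib responder matters in about 3.9% of trials, although near the threshold it does reverse the result. The off-drug counts assume a last dose on the day of Visit 7, and any result near Day 92 assumes no look-back for prior rescue.

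The correction is worth making because the rule determines the primary variable and is easy to repair.

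**What to change.** Add two sentences to SAP 8.4.1 for the primary analysis:

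1. A scheduled Visit 7 assessment that lies in the analysis window and has not been set to missing is the Day 84 value whenever it exists.
2. An unscheduled assessment may fill the Day 84 slot only when no such value exists, and only if it was taken no later than three days after the final study drug intake.

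The first sentence does most of the work. Extending the three-day limit alone would remove only 2 of the 9 no-rescue pairs within the protocol tolerance. The limit should not be applied to a completer's scheduled Visit 7, because that would discard an observed, in-window primary value and replace it by imputation. Referring to final intake keeps visits during temporary interruptions from being dropped.

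The cost is two sentences and a programming check, with no new data collection. A few completers without a Visit 7 score may move from a late off-drug value to imputation.

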6.9.2 Rescue Medication

In the event of a disease flare or AD symptoms defined as any worsening of AD to an vIGA \geq 3 requiring escalation of treatment confirmed by an investigator, which cannot be tolerated by the study participant, topical rescue medication as defined below may be used for a timeframe of several days at the discretion of the investigator. Before topical treatment for AD (= rescue medication) is initiated, the frequency of emollient use should be increased to try to control AD symptoms and efficacy assessments should be performed (see below and Section 8.1 [Unscheduled visit]).

Defined rescue medication for this study is the methylprednisolone aceponate (Advantan[®] cream). Only if Advantan cream is not available in the respective country, an alternative TCS with similar potency may be used (see WHO definition for potent corticosteroids group III, such as betamethasone, fluclorolone, desoximetasone, fluocinolone acetonide, budesonide, mometasone, beclomethasone, hydrocortisone aceponate). If TCSs are not tolerated or their use is not advisable, the topical TCIs pimecrolimus 1% (Elidel[®] cream) or tacrolimus (Protopic[®] 0.1% or 0.03% ointment) may be used.

The rescue medication is considered an auxiliary medicinal product (not an investigational product). The daily amount and frequency of application should be once daily for 1 week. If necessary, the duration of application may be extended to a maximum of 2 weeks. The use of rescue medication has to be documented in the CRF, providing information on product, dose, frequency and duration of therapy.

Topical rescue medication will be locally supplied/reimbursed by the sponsor during the study, including follow-up, according to the locally agreed process. Whenever possible, the efficacy assessments using the EASI, vIGA-AD and BSA affected by AD should be performed immediately before start of topical rescue therapy and at its end. Site visits

(scheduled or unscheduled) are therefore strongly recommended before start of rescue treatment.

If topical rescue medication is used, study intervention (zabedosertib or placebo) will be continued and study visits performed according to the SoA (see Section 1.3).

6.9.3 **Prohibited Medication and Therapies**

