4.2.4 Supplementary Analyses

Handling of use of rescue medication

The following supplementary analyses will be performed on the PPS to further assess the influence of rescue medication use on the EASI 75 response.

The analysis will be performed with a different handling of the following intercurrent event:

• Use of topical rescue medication: At Day 56 (Visit 6) or later (until Day 84 (Visit 7) or end of treatment if before Day 84 (Visit 7)): analyze study participant as non-responder (composite strategy)

Before Day 56 (Visit 6): disregard use of topical rescue medication (treatment policy strategy)

Use of rescue medication will be handled for supplementary analyses as outlined in the following:

The study participant is considered a non-responder in case of rescue medication use between the EOT visit and

- Baseline,
- 2 weeks after baseline,
- 4 weeks after baseline.

One additional analysis will be performed where rescue medication does not trigger the classification as non-responder at all to assess the effect of combined treatment of zabedosertib with topical AD medication.

If rescue medication does not trigger the classification as non-responder, the EASI 75 response will be based on the EASI scores collected after use of rescue medication.

Participants who take SoC medication or who discontinue study intervention due to lack of efficacy will still be counted as a non-responder for the time points after SoC use or discontinuation of study intervention due to lack of efficacy as described above.

The EASI score at time points after discontinuation of treatment due to other reasons not related to lack of efficacy or otherwise missing values will be imputed using "worst case" and last observation carried forward as described in Section 4.2.3. No multiple imputation approach using logistic regression will be performed for the supplementary analysis due to potential scarceness of participants continuing until Day 56 (Visit 6) without any rescue medication.

All other intercurrent events will be handled as described for the primary estimand.

Analysis on FAS

The EASI 75 response will be analyzed on the FAS according to the supplementary estimand (refer to Section 1.1). Imputation techniques in case of missing EASI 75 response information at Day 84 (Visit 7) will be as for the primary analysis.

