4.4 Other Endpoint(s) Analysis

4.4.1 Achievement of EASI 75 response up to Week 8 (Day 56)

Generally, the EASI 75 response over time will be analyzed similarly to the analyses for Day 84 (Visit 7) but restricted to those approaches where the intercurrent event "use of rescue medication" is handled similary between Day 1 (Visit 3) and Day 84 (Visit 7) to have comparable estimates over time. The analysis will be done according to the exploratory estimand for all time points (refer to Section 1.1). In detail, the following analyses will be performed for all time points (refer to Table 4-1):

- PPS, B_2.1, B_2.2 ("use of rescue medication" is handled as non-response for all following time points),
- FAS, B_7.1 and B_7.2 ("use of rescue medication" is handled as non-response for all following time points).

In addition, an analysis over time will be performed on the PPS where rescue medication does not trigger the classification as non-responder at all to assess the effect of study intervention on top of topical AD medication:

• PPS, B_5.1 and B_5.2 ("use of rescue medication" is ignored for all time points).

For details with respect to data handling and the imputation strategy refer to Section 8.4.

The probabilities for EASI 75 response at Day 84 (Visit 7) by treatment and the difference between treatments as derived from the Bayesian analysis will be plotted including 95% credible intervals for all analyses as summarized in Table 4-1.

Furthermore, the probabilities for EASI 75 response over time by treatment and the difference between treatments as derived from the Bayesian analysis as described above will be plotted including 95% credible intervals for the following analyses in one plot (for numbers refer to Table 4-1):

- PPS, B_2.1 + B_2.2 and B_5.1 + B_5.2,
- FAS, B_7.1 + B_7.2.

The other binary efficacy endpoints will be analyzed similarly.

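### The SAP's rule for choosing among assessments in a visit window conflicts with its rescue-ignoring analyses (B_5, C_3) for participants first rescued shortly before a planned visit

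*SAP*

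**What the plan says.** SAP 8.4.1 handles efficacy data in two stages. The first sets scores after systemic standard of care, or after rescue from a given visit onward, to missing. The second assigns assessments to visits and opens with "Then the following data handling steps will be performed for all participants". Its basic rule is "If several assessments fall into the same visit window the one closer to the planned visit day will be taken", with an exception where rescue preceded at least one of the assessments. In that case: "If there is still an assessment(s) without prior rescue medication use the one closest to the planned visit day will be selected". If every assessment in the window follows rescue: "Otherwise, the one with greater distance to prior rescue medication use will be selected".

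SAP 4.2.4 plans an analysis in which rescue never triggers non-response (B_5.1-5.2 in Table 4-1). Its purpose is "to assess the effect of combined treatment of zabedosertib with topical AD medication", and for it "the EASI 75 response will be based on the EASI scores collected after use of rescue medication". SAP 4.4.1 carries B_5 to all time points and says that rescue use "is ignored for all time points". Table 4-2 and SAP 4.4.2 set up the continuous counterpart, C_3.1-3.4, in which rescue is likewise disregarded.

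Protocol 6.9.2 asks that, where possible, EASI, vIGA-AD and BSA "should be performed immediately before start of topical rescue therapy and at its end". It strongly recommends a site visit, scheduled or unscheduled, before rescue begins.

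**The concern.** Under Protocol 6.9.2, a pre-rescue assessment followed within days by the planned visit is an expected pattern. When both fall in one window, SAP 4.2.4 calls for the later, post-rescue score and SAP 8.4.1 selects the earlier, pre-rescue one. Rescue is tied to a worsening to vIGA-AD 3 or more, so the selected score is typically a flare score, which is not what an analysis of drug plus topical therapy should use.

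B_5 and C_3 are the only inferential analyses of that combined effect; SAP 4.4.4 and 4.4.5 add only descriptive summaries of raw values. Two programmers, one following 4.2.4 and the other 8.4.1, would derive different datasets, and a choice between them made after unblinding would be post hoc. The gap is clearer for C_3: the explicit sentence in 4.2.4 names only EASI 75, so C_3 rests on the general statement that rescue is disregarded.

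**Working it through.** The plan gives no figure for this point. Its power statement (at least 90% with 38 and 19 evaluable, response rates 0.49 and 0.16, Beta(1,1) priors, posterior threshold 0.90) reproduces at 0.910 by exact enumeration and does not depend on the point.

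**Step 1: the rule applied literally.** The Day 84 window in SAP Table 8-3 is Days 76 to 92. The selection rule puts no look-back limit on prior rescue, so it is read here as any earlier use since treatment start.

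- Rescue starts Day 78, unscheduled visit Day 78 before rescue, scheduled visit Day 84: the Day 78 pre-rescue score is selected. This conflicts with 4.2.4.
- Rescue starts Day 65, only the Day 84 visit lies in the window: the post-rescue Day 84 score is used. No conflict.
- Rescue starts Day 20, visits on Days 80 and 84: both follow rescue, and the one further from it, Day 84, is used. No conflict.

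The conflict therefore needs two things: a first rescue start inside the window before the planned visit, and a pre-rescue assessment in the same window.

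**Step 2: days at risk.** For a visit on day v and a window opening on day w, the days at risk are w to v − 1, out of v − 1 earlier days.

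- Day 84 visit: 84 − 76 = 8; 8/83 = 9.6%.
- Visit at the protocol limits of ±3 days: Day 81 gives 5/80 = 6.3%; Day 87 gives 11/86 = 12.8%.
- Four post-dose windows, visits on the planned days: (14 − 10) + (28 − 21) + (56 − 49) + (84 − 76) = 4 + 7 + 7 + 8 = 26; 26/83 = 31%. This is the share of days on which a first rescue start could affect one of the by-visit results.

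**Step 3: participants affected at Day 84.** The documents give no rescue rate. Assume first rescue is uniform over time, 10% to 60% of participants use rescue, and each affected participant has a pre-rescue visit in the window. The affected share is rescue rate × 8/83.

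- 10%: 0.10 × 8/83 = 0.96%, about 0.4 of 38 and 0.2 of 19.
- 60%: 0.60 × 8/83 = 5.8%, about 2.2 of 38 and 1.1 of 19.

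If prior rescue were read with a shorter look-back, more participants would be affected, because someone rescued earlier could again count as not previously rescued.

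**The case against.** The best defence is that the SAP already answers the question. The sentence in 4.2.4 is specific to the rescue-ignoring analysis and can be taken to override a general rule for multiple assessments. The opening paragraph of 8.4.1 also excepts the combined-effect analysis from the principle that favourable post-rescue values are left out, and that principle is the evident reason for preferring pre-rescue scores. This shows what the authors intended. It does not settle the text: the exception leads into the set-to-missing stage, the selection step follows separately for all participants, and the exception is not repeated there. For C_3 there is no specific sentence to do the overriding.

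A second defence is redaction. Most of 8.4.2-8.4.3 is blacked out and figures near the rule are not shown, so an exemption there cannot be excluded. SAP 8.4.1 describes those sections as covering imputation after an intercurrent event, not selection among observed scores, so a cure there is unlikely.

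Third, the analyses are supplementary in an exploratory study and few participants are involved. That stands, and it limits the weight of the point.

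A reader might infer more than the documents support:

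- That B_5 and C_3 as a whole use pre-rescue scores and so fail to estimate drug plus topical therapy. They do not: with a single assessment in the window, or only post-rescue ones, a post-rescue score is used.
- That the smaller placebo arm makes the error favour zabedosertib, by about 5 points (2/19 − 2/38 = 10.5 − 5.3 = 5.3). This needs two affected participants in each arm, for example from about 8 rescue starters after Day 56 in each: 8/19 = 42% on placebo against 8/38 = 21% on zabedosertib. With equal rates, 1/19 = 2/38 and the shift is zero. It also needs every affected participant to be an EASI 75 responder by Visit 7, at most about 8 days after rescue began.

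**Conclusion.** The inconsistency is real but narrow. Read literally, SAP 8.4.1 gives B_5.1-5.2 and C_3.1-3.4 the wrong score for participants first rescued inside a window who also have a pre-rescue assessment in it. Under the assumptions in the working, that is about 1-6% of each arm at Day 84, with further cases possible in the by-visit results. The documents contain no rescue rates by arm, so neither the direction nor the size of a bias between arms can be stated. The primary analysis B_1.1, which does not ignore rescue at or after Day 56, is not in question, and no sample size or power figure changes. The correction is still worth making, because the protocol encourages the triggering pattern and the two SAP sections lead to different datasets.

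**What to change.** Add one sentence to SAP 8.4.1, at the selection rule: for B_5.x and C_3.x, the valid on-treatment assessment closest to the planned visit day is used regardless of rescue medication use. Leave the selection rule for all other analyses as it is; nothing here shows it to be defective for them. If the redacted part of 8.4.2-8.4.3 already contains such an exemption, a cross-reference at the selection rule is enough. The cost is that sentence and one condition in the derivation program, to be settled before unblinding.
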